#### **4.8 Prior and Concomitant Medications**

Concomitant medications will be analyzed using the SAF. Concomitant medications will be coded using the World Health Organization-Drug Dictionary (WHO-DD B3) Version March 2020 and will be classified by Anatomical Therapeutic Chemical (ATC) categories.

Medication start and stop dates will be compared to the date of first dose of study medication to allow medications to be classified as either Prior only, both Prior and Concomitant, or Concomitant only. Medications starting after the completion/withdrawal date will be listed but will not be classified or summarized. Medications that start and stop prior to the date of first dose of study medication will

be classified as Prior only. If a medication starts before the date of first dose of study medication and stops on or after the date of first dose of study medication, then the medication will be classified as both Prior and Concomitant. Medications will be classified as Concomitant only if they have a start date on or after the date of first dose of study medication.

If medication start and/or stop dates are missing or partial, the dates will be compared as far as possible with the date of first dose of study medication. Medications will be assumed to be Concomitant only, unless there is clear evidence (through comparison of partial dates) to suggest that the medication started prior to the first dose of study medication. If there is clear evidence to suggest that the medication started prior to the first dose of study medication, the medication will be assumed to be both Prior and Concomitant, unless there is clear evidence to suggest that the medication stopped prior to the first dose of study medication. If there is clear evidence to suggest that the medication stopped prior to the first dose of study medication, the medication will be assumed to be Prior only.

Prior and concomitant medications as recorded in the Concomitant Medication eCRF will be presented in by-patient data listing. Listing will include ATC Level 1/Treatment Name/Name, dose, frequency and route, start/stop date and classification (prior, previous or both).

#### 4.9 Treatment Exposure

Descriptive statistics for exposure will be presented for all subjects in SAF. Number and percentage of subjects received any amount of study drug will be summarized by treatment group and overall.

By-subject listing of drug exposure data as recorded on eCRF will be provided for SAF.

#### 4.10 Immunogenicity

Immunogenicity analyses will be conducted on IAS as defined in Section 4.5. In case a subject contracts SARS-CoV-2 after vaccination (seropositivity for N-Ab and/or documented SARS-CoV-2 infection ) or receives an approved COVID-19 vaccine , immunogenicity data collected from such subject will be excluded from immunogenicity analyses from that time point on.

Summaries will be provided by visit and treatment group for each immunogenicity endpoint as indicated in [IA: Interim analysis. FA: Final analysis.](#)

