4.2.3. Exploratory endpoints

The exploratory objectives of this study are to provide preliminary evidence on kinetics of immune response for 3 doses (namely 5×10^{10} , 1×10^{11} and 2×10^{11} viral particles) of GRAd-COV2 either in healthy adults or in elderlies. Kinetics will be described as the variation of humoral and cellular immune response at time of enrollment and eventually at week 2, 4, 8, 12 and 24 after vaccination in each arm. Several T cells assay will be performed to identify T cell subset mainly involved in the response to vaccination and to evaluate their polyfunctionality and phenotypic profile. Level of Neutralizing antibodies (nAb) to GRAd32 will be measured in serum at time of enrollment, 4 and 24 weeks after vaccination to evaluate any potential impact on vaccination efficiency. A correlation between humoral and cellular immune response will be evaluated. Within-the-cohort comparisons will be carried out to assess difference in immune response according to different doses in the same population. Across-the-cohort comparison will be carried out to assess whether elderlies and adults have different pattern of immune response after vaccination at different end points.

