## 1 INTRODUCTION

The analyses described in this SAP are based upon the following study documents:

- Study Protocol, Version 2.0 (September 8, 2020)
- electronic Case Report Form (eCRF), Version 4 (generated on August 4, 2020)
- DSMB Charter, Version 2.0

Per protocol, the collected data will be analyzed and reported in three steps according to stages achieved during the course of the study, ie:

Delivery 1: Interim Analysis 1

A report on safety and immunogenicity at 4 weeks for Adults-Cohort will be developed; this report will include:

- a. an analysis of safety issue in the three adults-arms;
- b. pivotal considerations for authorizing enrollment in the Elderlies-Cohort;
- c. a preliminary analysis of immunogenicity in the three adults-arms aimed at identifying the most convenient dose to be used in the eventual phase 2/3 trial.

Delivery 2: Interim Analysis 2

A report on safety and immunogenicity at 4 weeks for Elderlies-Cohort will be developed; this report will include pivotal considerations on:

- a. an analysis of safety issues in the three elderlies-arms
- b. a preliminary analysis of immunogenicity in the three elderlies-arms aimed at identifying the most convenient doses to be used in the eventual phase 2/3 trial.
- c. comparison of safety and immunogenicity between adults and elderlies (across the cohort comparison) to define the most convenient dose to be used either in general population or special groups at risk.

Delivery 3: Final Analysis

Within one year since LSLV final report will be produced including:

- a. Final analysis on safety and immunogenicity at 24 weeks after vaccination in Adults-Cohort
- b. Final analysis on safety and immunogenicity at 24 weeks after vaccination in Elderlies-Cohort

Analyses described hereafter will cover all these three stages of the study with applicable closures on selected analyses if a stage requires.

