### 4.2 General Presentation Considerations

The overall outline of the scheduled assessment and other study procedures can be found in the Schedule of Assessment, [Table 5](#). In the following, the data handling conventions should be interpreted within the framework of the Schedule of Assessment.

The date of Enrolment Visit (Time 0) is defined as Day 1. All other study days will be labeled relative to Day 1.

- For observation/event dates on or after Day 1, study day for an observation/event date is derived as:  
Observation/event date – visit Time 0 date + 1 day, which could be Day 1, Day 2, Day 3, etc.
- For observation/event dates prior to Day 1, study day for an event date is derived as:  
Observation/event date – visit Time 0, which could be Day -1, Day -2, etc., referring to 1 day, 2 days, etc., prior to Day 1, respectively.
- Day 0 is not defined.

Baseline is considered as the result of last non-missing evaluation before vaccine administration, unless specified otherwise.

End of Study is defined as the last available post-treatment assessment.

Continuous data will be summarized in terms of the mean, standard deviation (SD), median, minimum, maximum and number of observations, unless otherwise stated.

Count data will be summarized in terms of the median, lower and upper quartile, minimum, maximum and number of observations, unless otherwise stated. Geometric mean titer will be provided also for result in titer.

Categorical data will be summarized in terms of the number of subjects providing data at the relevant time point (n), frequency counts and percentages. Any planned collapsing of categories will be detailed in the SAP text and the data displays.

The minimum and maximum will be reported to the same number of decimal places as the raw data recorded in the database. The mean, median, lower quartile and upper quartile will be reported to one more decimal place than the raw data recorded in the database. The SD will be reported to two more decimal places than the raw data recorded in the database. In general, the maximum number of decimal places reported shall be four for any summary statistic. Confidence intervals will be presented to one more decimal place than the raw data.

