#### [\[1\] AE and Categorical Safety only](#)

**Table 3** at Section 4.2. Immunogenicity evaluations will be assessed as shown in the Schedule of Assessments (Appendix 6.1).

Concentration below lower limit of quantification (BLQ) will be set to LLOQ/2 = 1.9 for summary calculations and graphical presentation. BLQ values will be listed as is in the source. Results of anti-S-Ab concentration will be summarized descriptively as indicated in Section 4.2.

Categorical results of anti-S-Ab, anti-N-Ab and PBMC ELISpot test will be tabulated by number and percentage of subject in each category.

Count data (micro neutralization test [titer]) will be summarized descriptively as indicated in Section 4.2.

Numeric assay result will be derived using the dilution factor from source data, ie 1:10 = 10, 1:20 = 20, etc. For result below limit of detection (LOD) which reported as <1:10 numeric result will be set to five (5) for summaries and graphical analyses.

Geometric mean titer for time point j will be calculated as

$$GMT_j = e^{\frac{\sum_{i=1}^{n_j} \ln(x_{ij})}{n_j}}$$

, where  $x_{ij}$  is the titer observed at time point j for subject i, and  $n_j$  is the number of observations at time point j.

To visualize the comparison between treatment groups the following graphs will be presented:

- Mean concentration – time profile of anti-S-Ab on semi-logarithmic scale.
- Individual concentration – time profiles (spaghetti plot) of anti-S-Ab on semi-logarithmic scale.
- By-visit combined plots (box + scatter) for micro neutralization and PBMC ELISpot results.

Inclusion of subjects for ELISpot analyses will depend on validity of the negative control results and be decided on case by case basis. Specifically, for the IFN $\gamma$  ELISpot test on fresh PBMC at week 2, number of pools with positive results obtained in PBMC ELISpot test will be assigned into two categories such as negative or positive. Result will be negative if number of positive pools is zero and positive if number of positive is greater than or equal to one.

ELISpot assay results on frozen PBMC samples obtained on Week 2, will be provided by the sponsor (outside of EDC system used in the study) and will be analyzed with other assay results recorded in EDC.

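### SAP 4.10 drops data after infection or licensed vaccination and summarises each visit on whoever remains, so late-versus-early immunogenicity contrasts mix change in response with change in membership, and no same-subject summary is planned

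*SAP*

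**What the plan says.** SAP 4.10 defines the exclusion event as infection after vaccination (N-antibody seropositivity and/or documented infection) or receipt of an approved COVID-19 vaccine. From then on, "immunogenicity data collected from such subject will be excluded from immunogenicity analyses from that time point on"; data from before the event stay in.

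The summaries are organised visit by visit: "Summaries will be provided by visit and treatment group for each immunogenicity endpoint". The divisor in the geometric mean titre formula "is the number of observations at time point j", so it changes with attendance and exclusion. For anti-S concentration, SAP 4.2 applies: "Continuous data will be summarized in terms of the mean, standard deviation (SD), median, minimum, maximum and number of observations". The anti-S figures are "Mean concentration – time profile of anti-S-Ab on semi-logarithmic scale" and "Individual concentration – time profiles (spaghetti plot) of anti-S-Ab on semi-logarithmic scale". Neutralisation and ELISpot are drawn as box-and-scatter plots by visit.

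Entry to the immunogenicity set (SAP 4.5) needs only one post-baseline value, so no constant set of participants is defined across visits.

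On purpose, Protocol 4.2.3 says "Kinetics will be described as the variation of humoral and cellular immune response", from enrolment to week 24 in each arm. The final report includes "Final analysis on safety and immunogenicity at 24 weeks after vaccination in Elderlies-Cohort", and the same for adults.

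Protocol 10.2 plans change from baseline and, if normality is shown, a regression model for correlated measures. SAP 4.10 contains neither, although the SAP does specify change from baseline for laboratory values (4.11.3) and vital signs (4.11.5).

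**The concern.** Setting aside data collected after infection or another vaccine is a sensible way to describe the response to the study vaccine alone. The difficulty is what follows. If some participants contribute at W4 but not at W24, the two visit summaries describe different people, and their ratio is not the average decline of any fixed group.

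Persistence to week 24 is a final deliverable and kinetics a stated exploratory aim, so this ratio is what a reader will take from the tables. With 15 planned per arm, a few exclusions can move it.

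Both exclusion events also depend on calendar time, and Protocol 5 starts the elderly arms only after the 4-week safety decision on Arm-1. Exclusions may therefore differ between the cohorts that Protocol 10.2 compares at the same visits.

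**Working it through.** **Inputs from the documents.** 15 per arm (SAP 3.1); post-event data dropped, earlier data kept, summaries by visit (SAP 4.10); neutralisation at W4 and W24 only (Protocol 4.2.2, SAP Table 5). No exclusion count, antibody SD or dropout rate is given, so there is no planned figure to reproduce.

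**Assumptions, for illustration only.** 3 or 5 of 15 removed between W4 and W24; between-subject SD 0.3 to 0.5 log10; within-subject SD 0.15 log10; true W24/W4 ratio 0.50.

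**Step 1: the composition term.** On the log10 scale, let n contribute at W4 and m of them be excluded by W24. Then

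W24 mean (remaining) − W4 mean (all) = [W24 mean − W4 mean, both in the remaining] + [W4 mean (remaining) − W4 mean (all)].

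The second bracket is pure composition and equals (m/n) × [W4 mean (remaining) − W4 mean (excluded)]. This is an identity and needs no distribution. Suppose the excluded had a W4 geometric mean f times lower than those remaining. The apparent ratio is then 0.50 × f^(m/n):

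| m of 15 | f = 1 | f = 1.5 | f = 2 | f = 3 |
|---|---|---|---|---|
| 3 | 0.50 | 0.54 | 0.57 | 0.62 |
| 5 | 0.50 | 0.57 | 0.63 | 0.72 |

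For example, m = 5 and f = 2: (5/15) × 0.301 = 0.100; 10^0.100 = 1.26; 0.50 × 1.26 = 0.63. If the excluded were instead 2 times higher, the same case gives 0.50 / 1.26 = 0.40.

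**Step 2: simulation.** Removal weight was exp(−b × standardised response), with b = 0.5 or 1. By-visit geometric means gave ratios of 0.54 to 0.62 with 3 removed and 0.57 to 0.72 with 5 removed. The planned anti-S summary uses arithmetic means, and on that scale the range over all these settings was about 0.53 to 0.63. The same participants' own geometric mean ratio was 0.50 throughout.

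**Step 3: random removal (b = 0).** There is no bias. With SD 0.5 and 3 removed, the variances of the log10 ratio are:

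- By visit: 0.25 × (1/12 − 1/15) + 0.0225 × (1/12 + 1/15) = 0.00417 + 0.00338 = 0.00754, so SE 0.087 (0.086 simulated).
- Same participants: 2 × 0.0225 / 12 = 0.00375, so SE 0.061.

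**Step 4: limits of pairing.** The 0.50 in step 2 follows from giving everyone the same underlying decline and linking removal to level only. If decline varies between participants (assumed SD 0.15 to 0.25 log10) and faster waners are likelier to leave, the paired ratio is roughly 0.52 to 0.60, as biased as the by-visit ratio. If removal is linked to the measured W4 value, the paired ratio is about 0.47 to 0.49.

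**The case against.** The strongest reply is that this is a descriptive study with no hypothesis test (SAP 4.13), that kinetics are exploratory, and that observed-case summaries by visit are a legitimate convention. All of that stands, and it limits the weight of the point. It does not remove the composition term, which sits in the description itself.

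Several planned items help in part:

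- **Anti-S individual profiles.** They show each participant's course and where it stops. It would be wrong to infer that nothing planned follows the same people over time. The plot gives no summary or interval, however, and neutralisation and ELISpot have no equivalent.
- **Number of observations.** SAP 4.2 already requires it in the tables, so shrinking membership will be visible. Visibility is not correction.
- **Protocol 10.2.** Change from baseline and the conditional model are not carried into SAP 4.10. Change from baseline would help little here in any case. Seropositive volunteers are excluded at entry (Protocol 6.5), so anti-S baselines should lie near the assay floor and the change would largely repeat the level.

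A reader might also infer that the late means will be too high because weak responders get infected or seek another vaccine. The documents do not support a direction. They give no link between response and exclusion, and nothing says that participants are told their titres.

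**Conclusion.** The point holds as a gap in the planned output. Whenever anyone is excluded between W4 and a later visit, the by-visit contrast carries a composition term, and SAP 4.10 has no numerical summary free of it. For anti-S and ELISpot this concerns the later visits against W4; for neutralisation it concerns the single W24/W4 pair.

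Its size and direction cannot be determined from the documents. The apparent 0.54 to 0.72 for a true 0.50 rests on the assumed SDs, on 3 to 5 of 15 removed, and on removal linked to low level. With no exclusions there is no artefact; with random exclusions there is only lost precision.

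Three stronger readings should be avoided:

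- That persistence will be overstated. This needs selective loss of low responders, which is not documented.
- That early visits hold all 15 per arm. SAP 4.5 can remove participants for interfering deviations, ELISpot inclusion is decided case by case, and an exclusion event can occur before W4.
- That a same-subject ratio is unbiased in general. Step 4 shows that it is not.

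This is a cheap and worthwhile improvement. The exclusion rule itself is not at fault.

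**What to change.** Add to SAP 4.10, beside the existing by-visit summaries:

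1. One table per assay with the geometric mean ratio to the same participant's W4 value and its 95% CI, in participants contributing at both visits. For anti-S and frozen-sample ELISpot, give W8, W12 and W24; for neutralising antibody, W24 only. Base statements about persistence on this table, with the limits below.
2. The number excluded and the reason (infection or approved vaccine), by visit and arm.
3. The number contributing at each visit, printed under the anti-S mean profile.

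The cost is one extra table per assay and a short exclusion table, all from data already collected. State three limits with the results. The ratio describes only those still contributing at the later visit. It removes composition related to response level, but not bias from exclusion linked to the rate of waning. Values set to the floor (1.9 for anti-S, 5 for neutralisation) compress the ratio, so report how many there are at each visit.

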4.2.2. Secondary endpoints (immunogenicity)

The secondary endpoint for the study is the assessment of cellular and humoral immune response elicited by the vaccine at different time weeks after the administration of three different doses of vaccine, namely 5×10^{10} , 1×10^{11} and 2×10^{11} viral particles, either in adults and elderlies. This include:

- A. CLIA to quantify antibodies to SARS-CoV-2 S-protein (anti-S-Ab) at week 2, 4, 8, 12 and 24 in adults who receive either 5×10^{10} , 1×10^{11} and 2×10^{11} viral particles;
- B. CLIA to quantify antibodies to SARS-CoV-2 S-protein (anti-S-Ab) at week 2, 4, 8, 12 and 24 in elderlies who receive either 5×10^{10} , 1×10^{11} and 2×10^{11} viral particles;
- C. CLIA to quantify antibodies to SARS-CoV-2 N-protein(anti-N-Ab) at week 2, 4, 8, 12 and 24 in adults who receive either 5×10^{10} , 1×10^{11} and 2×10^{11} viral particles;
- D. CLIA to quantify antibodies to SARS-CoV-2 N-protein(anti-N-Ab) at week 2, 4, 8, 12 and 24 in elderlies who receive either 5×10^{10} , 1×10^{11} and 2×10^{11} viral particles;
- E. SARS-CoV-2 micro-neutralization assay to quantify neutralizing antibody activity to the virus at week 4 and 24 in adults who receive either 5×10^{10} , 1×10^{11} and 2×10^{11} viral particles;
- F. SARS-CoV-2 micro-neutralization assay to quantify neutralizing antibody activity to the virus at week 4 and 24 in elderlies who receive either 5×10^{10} , 1×10^{11} and 2×10^{11} viral particles;
- G. Ex vivo IFN γ ELISpot responses to SARS-CoV-2 S-protein at week 2, 4, 8, 12 and 24 in adults who receive either 5×10^{10} , 1×10^{11} and 2×10^{11} viral particles
- H. Ex vivo IFN γ ELISpot responses to SARS-CoV-2 S-protein at week 2, 4, 8, 12 and 24 in elderlies who receive either 5×10^{10} , 1×10^{11} and 2×10^{11} viral particles

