### 3.2.2 Immunogenicity Variables

- Antibodies to SARS-CoV-2 S-protein (anti-S-Ab)
- Antibodies to SARS-CoV-2 N-protein(anti-N-Ab)
- SARS-CoV-2 micro-neutralization assay
- Magnitude of interferon gamma (IFN $\gamma$ ) ELISpot response (SFC/10 $^6$  PBMC)
- T-cell response (number of positive spike pools-only applicable for fresh PBMC at week 2)

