Percentages will be presented to one decimal place. Percentages will not be presented for zero counts. Percentages will be calculated using n as the denominator. If sample sizes are small, the data displays will show the percentages, but any textual report will describe frequencies only.

Changes from baseline in categorical data will be summarized using shift tables where appropriate.

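### SAP 4.10 uses anti-N positivity to exclude immunogenicity data but does not exempt the anti-N endpoint, so post-vaccination positives drop out of their own table

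*SAP*

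**What the plan says.** SAP 4.10 defines infection after vaccination as "seropositivity for N-Ab and/or documented SARS-CoV-2 infection", so an anti-N result is sufficient without any other evidence. For a subject who meets that definition, or who receives an approved COVID-19 vaccine, "immunogenicity data collected from such subject will be excluded from immunogenicity analyses from that time point on".

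The same section then states: "Summaries will be provided by visit and treatment group for each immunogenicity endpoint". It adds: "Categorical results of anti-S-Ab, anti-N-Ab and PBMC ELISpot test will be tabulated by number and percentage of subject in each category".

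Anti-N-Ab is one of the immunogenicity variables in SAP 3.2.2. Protocol 4.2.2 makes it a secondary endpoint, as item C, "CLIA to quantify antibodies to SARS-CoV-2 N-protein(anti-N-Ab) at week 2, 4, 8, 12 and 24 in adults", and as item D for the elderly cohort.

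Two presentation rules in SAP 4.2 also apply: "Percentages will be calculated using n as the denominator" and "Percentages will not be presented for zero counts". The first uses the number of subjects with data at the visit.

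**The concern.** The variable that triggers the exclusion is also one of the variables to be summarised after the exclusion. SAP 4.10 has no exemption for anti-N, and the SAP specifies no anti-N or infection summary on unexcluded data.

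This matters because anti-N is the one scheduled laboratory marker that can separate natural infection from vaccine response after dosing. The vector carries the S-protein (Protocol 3.4.2), so anti-S cannot do so. In Protocol Figure 9 and SAP Table 5, diagnostic SARS-CoV-2 serology is done at screening only, and no molecular test is scheduled. Molecular testing is prompted by symptoms (Protocol 7.3, 7.8 and 15.1.3). A subject who seroconverts without being tested can therefore be seen only in the anti-N results. Protocol 15.1.3 also wants exposure among vaccinees monitored so that disease enhancement can be assessed, and undocumented seroconversions are part of that exposure.

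**Working it through.** **Inputs.** There are 6 arms × 15 = 90 subjects, in agreement with SAP 3.1. Anti-N is sampled at T0 and at weeks 1, 2, 4, 8, 12 and 24 (SAP Table 5). The documents give no seroconversion rate, so the proportion p converting by week 24 is an assumption, taken from 1% to 10%. The plan states no figure on this point to reproduce.

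**Reading 1: the triggering sample is excluded.** A sample at visit j is kept only if no trigger occurred at or before j. A positive anti-N at j is itself a trigger at j. No kept sample can be positive, so the count is 0 for any p, and this step needs no assumption. Two limits apply:
- The rule concerns infection after vaccination, so a subject already positive at T0 is not clearly caught. Exclusion criterion 4 in Protocol 6.5 should make this rare.
- The zero applies to the positive category. The SAP does not list the categories, and an equivocal one, if reported, could be non-empty.

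Without the rule, the table could be expected to show:

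| Assumed p | Expected converters, 90p | P(at least 1 of 90) = 1 − (1 − p)^90 | P(at least 1 of 15) = 1 − (1 − p)^15 | Positives shown under the rule |
|---|---|---|---|---|
| 1% | 0.9 | 59.5% | 14.0% | 0 |
| 2% | 1.8 | 83.8% | 26.1% | 0 |
| 5% | 4.5 | 99.0% | 53.7% | 0 |
| 10% | 9.0 | 99.99% | 79.4% | 0 |

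**Reading 2: the triggering sample is kept and later ones are dropped.** Assume infection times spread evenly over 24 weeks, persistent positivity, complete sampling, and anti-N as the first sign of infection. For a visit at week t with the previous visit at week s:
- unexcluded proportion = p·t/24
- proportion shown = [p·(t − s)/24] / [1 − p·s/24]

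At week 24 (s = 12):
- p = 2%: 0.010/0.990 = 1.0%, against 2.0%
- p = 5%: 0.025/0.975 = 2.6%, against 5.0%
- p = 10%: 0.050/0.950 = 5.3%, against 10.0%

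At week 12 (s = 8) with p = 5%: 0.00833/0.98333 = 0.85%, against 2.5%.

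The positive count is no longer zero, but week 24 shows about half the unexcluded value and week 12 about a third.

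**Effect on the other summaries.** Under reading 1, expected n at week 24 is 90(1 − p) = 88.2, 85.5 and 81.0 for p = 2%, 5% and 10%, before any other loss. One subject is 1/15 = 6.7% of an arm. SAP 4.2 puts n in every by-visit table, so the fall is visible. Infection, receipt of an approved vaccine and a missing sample all reduce n in the same way, and the tables do not separate them.

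**The case against.** **The exclusion is sensible.** Infection or an outside vaccine confounds the anti-S, neutralisation and ELISpot responses. This stands, and the point does not dispute it.

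**A reader might infer that the plan would report no infections whatever happened.** The documents do not support that. The exclusion covers immunogenicity analyses only. Protocol 7.8 requires molecular testing for persistent fever and hospital admission for confirmed COVID-19. Protocol 9.1 counts hospitalisation as an SAE. SAP 4.11, 4.11.1 and 4.11.2 list all AEs and SAEs on the Safety Analysis Set. Documented infection therefore remains visible, and only undocumented seroconversion is lost.

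**A reader might infer that the plan hides how many subjects left the summaries.** It does not, because n is reported by visit and arm. Only the reason is missing.

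**A reader might infer that the table will show 0%.** SAP 4.2 suppresses percentages for zero counts, so it would print 0 alone. The zero also depends on reading 1. Under reading 2, adding first positives across visits could recover the converters, but no cumulative table is planned. A subject whose infection was documented before the first positive anti-N sample would still be missing.

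**A reader might want to count subjects wrongly censored after one false-positive anti-N result.** The documents give no assay specificity. Any such count would also need an assumption about whether errors are independent across a subject's six post-dose tests. The point does not rest on it.

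**The trial is descriptive.** SAP 4.13 plans no hypothesis tests and the primary endpoint is safety. That stands and limits the severity.

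**Conclusion.** SAP 4.10 is wrong as written for anti-N-Ab. On the plain reading, the post-vaccination positive count is 0 at every visit regardless of the true rate, except for anyone already positive at T0. On the other reading, only first positives are kept and later visits are understated, by about half at week 24 under the even-timing assumption. The SAP does not say which reading applies, and neither reports the endpoint correctly. The zero needs no numerical assumption. The expected counts and the understatement rest on the assumed 1% to 10% range and on the timing model.

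The practical loss is seroconversion not otherwise documented as infection, together with the reasons for falling n in the other immunogenicity summaries. **SHOULD-FIX**, because the endpoint is secondary and descriptive and no primary result depends on it.

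**What to change.** In SAP 4.10:

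1. Limit the infection exclusion to the anti-S, neutralisation and ELISpot summaries, and exempt anti-N-Ab from it.
2. State whether the triggering sample itself is excluded from those summaries.
3. Tabulate anti-N by visit, and cumulatively by arm, on all subjects in the Immunogenicity Analysis Set.
4. Report the number censored per arm and visit, with the reason: infection, approved vaccine or missing sample.

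A sensitivity table that requires confirmation of a positive anti-N result is optional. If used, it must say how a first positive at week 24 is handled. Neither Protocol Figure 9 nor SAP Table 5 schedules a later sample, and the week 48 visit named in Protocol 7.8 appears in neither.

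The cost is a few sentences and one or two tables on data already collected. No new sampling is needed.
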